2.3.2 Patient disposition

RAN will be used for the summary and listing of patient disposition.

Week 24 analysis

Based on the SCR, the number and percentage of patients screened will be presented. In addition, the primary reasons for screen failures will be summarized by presenting number and

percentage of screen failed patients by category. The number and percentage of subjects entered, completed, and failed in run-in will be summarized using the RUN. The reasons for run-in failures will be provided. The number and percentage of randomized subjects who completed the Epoch 3, who discontinued the Epoch 3 and the reasons for discontinuation will be presented for each treatment group using the RAN.

The number of randomized subjects included in each analysis set (FAS, SAF, and PPS) will be presented by treatment group. The number and percentage of subjects with protocol deviations as well as the criteria leading to exclusion from analysis sets will be presented in separate tables for the RAN. Subject exclusion from analysis sets will be listed with reasons for exclusion.

The number of randomized subjects included in each analysis set (FAS, SAF, and PPS) will also be presented by treatment group and glycemic status.

End of study analysis

The number of RAN subjects who entered Epoch 4, completed Epoch 4, and who discontinued Epoch 4 and the reasons for discontinuation will be presented for each treatment group.

Subject randomization number and whether they completed or were discontinued from Epoch 3 and/or Epoch 4 will be listed, with date of last dose and primary reason for discontinuation, including unblinding date if applicable, by 10 randomized treatment arms. Flags will be included to indicate misrandomized patients and forced randomization.

2.4 Treatments (study treatment, rescue medication, concomitant therapies, compliance)

2.4.1 Study treatment / compliance

Week 24 analysis

The duration of double-blind treatment exposure in Epoch 3 will be summarized by treatment group both descriptively in days (mean, standard deviation, minimum, Q1, median, Q3, and maximum) and by duration category in weeks (≤ 2 , $>2-4$, $>4-8$, $>8-12$, $>12-16$, $>16-20$, $>20-24$, and >24) for the SAF.

- Duration of exposure (days) = last dose date of Epoch 3 – first dose date + 1
- Duration of exposure (weeks) = (last dose date of Epoch 3 – first dose date + 1)/7

Overall subject-years on-treatment in Epoch 3 will be reported by each treatment group.

- Overall subject-years on-treatment = sum of duration of treatment exposure (in days) from all subjects / 365.25

The duration of double-blind treatment exposure excluding treatment interruptions in Epoch 3 will also be summarized descriptively and by duration categories as above.

- Duration of exposure excluding treatment interruptions (days) = last dose date of Epoch 3 – first dose date + 1 – number of days of treatment interruption

Treatment interruptions will be considered as following:

- For BID doses – patients taking 0 tablets for both morning and evening doses,
- For QD doses – patients taking 0 tablets for the morning dose,
- For Placebo – patients taking 0 tablets for both morning and evening doses.

Number and percentage of subjects with treatment interruption and permanent treatment discontinuations in Epoch 3 will be provided by reason for treatment interruption or discontinuation.

Duration of treatment interruption, frequency and duration of the PD after meal dose intake will also be summarized as appropriate.

End of study analysis

The duration of Epoch 4 will be summarized by treatment group both descriptively in days and by duration-category in weeks (≤ 4 , $>4-12$, $>12-24$, and >24) for subjects in the safety set who enter the study Week 24 to Week 48 period (Epoch 4), respectively.

- Epoch 4 duration of exposure (days) = last dose date – first dose date of Epoch 4 + 1
- Epoch 4 duration of exposure (weeks) = (last dose date – first dose date of Epoch 4 + 1)/7

Duration of treatment interruption, frequency and duration of PD after meal dose intake will also be summarized as appropriate.

The duration of overall treatment period (Epoch 3 + Epoch 4) will also be summarized by 10 randomized arms both descriptively in days and by duration-category in weeks (≤ 4 , $>4-12$, $>12-24$, $>24-36$, $>36-48$, and >48), respectively.

- Overall duration of exposure (days) = last dose date – first dose date + 1
- Overall duration of exposure (weeks) = (last dose date – first dose date + 1)/7

Number and percentage of subjects with treatment interruption and permanent treatment discontinuations in overall treatment period will be provided by reason for treatment interruption or discontinuation. Frequency and duration of PD after meal dose intake will be included for reporting as well.

2.4.2 Prior, concomitant and post therapies

Week 24 analysis

Prior medications are defined as any drugs taken and stopped prior to the first dose of study medication. Concomitant medications for Epoch 3 are any medications given at least once between the day of first dose of double-blind study medication and the end of Epoch 3, including those which started pre-BL and continued into the treatment period.

The number and percentage of subjects receiving prior and concomitant medications will be summarized by treatment group and overall in the SAF in separate tables by therapeutic class and preferred term.

The number and percentage of subjects taking rescue medication, and duration of exposure to rescue medication during Epoch 3 will be summarized by treatment group.

The number and percentage of subjects on anti-diabetic medications at BL (randomization visit) will be summarized by treatment, glycemic status, and medication types:

- Any anti-diabetic medication (insulin or OADs)
- Insulin
- OADs (used as single pills)
 - Metformin
 - SU - Sulfonylureas (including Sulfonamides)
 - AGIs
 - TZDs
 - DPP-4 inhibitors
- Combination of OADs
 - Phenformin + SU
 - Metformin + SU
 - Metformin + TZD
 - SU + TZD
 - Metformin + DPP-4i
 - Metformin + AGI
 - DPP-4i + TZD
- Other

The search criteria for the anti-diabetic medications by type are included in the appendix.

The use of prohibited medications, defined in Table 2-2 below, will also be summarized.

Table 2-2 Prohibited medication for reporting

Prohibited Medication	Drug record No. or ATC
Clarithromycin	00984601
Telithromycin	01548701
Itraconazole	00780701
Ketoconazole	00532501
Voriconazole	01510101
Posaconazole	01762801
Probenecid	00045101
Valproic Acid	00228501
Mefenamic Acid	00044201
SGLT2 inhibitors	A10BK

Prohibited Medication	Drug record No. or ATC
GLP-1 receptor agonists	A10BJ
Weight loss medication	A08A

End of study analysis

Concomitant medications for Epoch 4 are any medications given at least once between the start and the end of Epoch 4, including those which started before and continued into Epoch 4. Concomitant medications subjects take during Epoch 4 will be similarly summarized for subjects in SAF who enter Epoch 4.

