**Table 5-2 Prohibited medication**

Medication/product	Prohibition period	Action taken
St. John's wort (strong CYP3A inducer)	Entire study	Discontinue prohibited medication during the screening period once subject is eligible for participation in the study
GLP-1 agonists	Entire study	Discontinue prohibited medication during the screening period once subject is eligible for participation in the study
SGLT2 inhibitors other than study medication	Entire study	Discontinue prohibited medication during the screening period once subject is eligible for participation in the study
Pharmacologically active weight-loss medication	Entire study	Discontinue prohibited medication during the screening period once subject is eligible for participation in the study

Some medications or products must be used with caution:

- Use of grapefruit juice (strong inhibitor of CYP3A4) should be discouraged and its consumption must not happen within 2h of study medication intake.
- Use of antibiotic or antifungal medications that are strong inhibitors of CYP3A4 should be limited to 10 days during the study. Examples of such medications are clarithromycin, telithromycin, itraconazole, ketoconazole, voriconazole or posaconazole.
- Use of strong UGT inhibitors such as probenecid, valproic acid or mefenamic acid should be limited to 10 days during the study.

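### SAP Table 2-2, which defines the prohibited-medication summary, omits St. John's wort and lists as prohibited nine inhibitors that the protocol only limits to 10 days

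*SAP*

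**What the plan says.** Protocol section 9.3 plans a summary of prohibited-medication use and does not define the term there. SAP section 2.4.2 supplies the definition: "The use of prohibited medications, defined in Table 2-2 below, will also be summarized". The table is headed "Table 2-2 Prohibited medication for reporting". It has 12 rows: nine drugs identified by drug record number and three classes identified by ATC code. No row carries a duration condition.

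Protocol section 5.5.8 has two parts. The first is protocol Table 5-2, whose four entries are barred for the whole study. Its first entry is "St. John's wort (strong CYP3A inducer)". The others are GLP-1 agonists, SGLT2 inhibitors other than study drug, and active weight-loss medication.

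The second part stands below the table and opens differently: "Some medications or products must be used with caution". Two of its items concern the drugs at issue here:
- On the CYP3A4 side: "Use of antibiotic or antifungal medications that are strong inhibitors of CYP3A4 should be limited to 10 days during the study". The protocol then names six drugs by way of example.
- On the UGT side, where three drugs are named: "Use of strong UGT inhibitors such as probenecid, valproic acid or mefenamic acid should be limited to 10 days during the study".

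**The concern.** A table of prohibited-medication use is read as a table of protocol breaches, so the SAP definition should select what the protocol bars. This one departs from the protocol in both directions. It takes in drugs whose short use the protocol accepts, and it leaves out the first entry in the protocol's own table.

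The SAP's document history gives agreement with the protocol as the reason for an update to this list, so the mismatch does not look intended. SAP section 4, which records changes to protocol-specified analyses, mentions only hsCRP.

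At stake is how one descriptive table reads. Subjects could be shown as users of prohibited medication when they kept within the protocol. A subject who took St. John's wort would not be shown as one.

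**Working it through.** The plan gives no figure to reproduce. The check compares the two lists entry by entry.

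| Item | Protocol section 5.5.8 | SAP Table 2-2 |
|---|---|---|
| St. John's wort | Table 5-2, whole study | absent |
| GLP-1 agonists | Table 5-2, whole study | listed |
| SGLT2 inhibitors | Table 5-2, whole study | listed |
| Weight-loss medication | Table 5-2, whole study | listed |
| Clarithromycin, telithromycin, itraconazole, ketoconazole, voriconazole, posaconazole | caution, 10-day limit | listed, no duration condition |
| Probenecid, valproic acid, mefenamic acid | caution, 10-day limit | listed, no duration condition |

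**Counts**
- SAP rows: 6 CYP3A4 inhibitors + 3 UGT inhibitors + 3 classes = 12.
- Rows that are time-limited caution items: 6 + 3 = 9, and 9/12 = 75%.
- Protocol Table 5-2 entries missing from the SAP: 1 of 4 = 25%.

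**Is short use really permitted?** Yes, on two readings. The 10-day limit in section 5.5.8 implies it, and exclusion criterion 22 bars only chronic use of strong CYP3A4 and UGT inhibitors.

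**Does the SAP apply a duration rule elsewhere?** None is stated. Section 2.4.2 treats a medication as concomitant if it was given even once in the Epoch 3 window. A one-day course of clarithromycin would therefore meet the Table 2-2 definition.

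**Does a version difference explain it?** Not visibly. The SAP introduction refers to the original protocol, but the change list for protocol Amendment 1 does not mention section 5.5.8.

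**Would a plain 10-day filter solve it?** Not by itself. SAP section 5.1.3 imputes a missing end day as the earlier of treatment end and month end. For months after the month of treatment start, it imputes a missing start day as the first of the month. Take a 31-day month of that kind, with the subject on treatment throughout, and the SAP section 2.1.1 duration formula (end − start + 1):
- Both days missing: 31 − 1 + 1 = 31 days.
- Start known as the 5th, end day missing: 31 − 5 + 1 = 27 days.
- Start on day s, end day missing: the imputed length exceeds 10 when 31 − s + 1 > 10, that is, when s ≤ 21.

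A course that in fact lasted a few days could thus be flagged as over the limit only because a day was not recorded.

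**The case against.** Tracking the nine drugs is not itself an error. They appear in a protocol section headed as prohibited medication, use beyond 10 days breaches the stated limit, and a broad screen for any use is defensible. This stands, and it narrows the fault on that half to the label and the missing duration condition. It does not explain the absence of St. John's wort.

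Nor would recorded St. John's wort use vanish from the report. Protocol section 5.5.7 requires every medication taken after enrolment to be recorded, and SAP section 2.4.2 tabulates prior and concomitant medications by class and preferred term. The use would appear there, though not flagged as prohibited. This also stands.

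A reader might infer that, because protocol section 5.6.2 requires study treatment to stop after prohibited use and SAP section 5.4 excludes such users from the PPS, the faulty list distorts both. The documents do not support that:
- Section 5.6.2 refers to protocol section 5.5.8, which is what investigators apply, and not to the SAP table.
- Exclusion criterion 4 cites protocol Table 5-2, so EXCL04 most naturally follows that list.
- SAP section 5.4 leaves the deviation details to a separate edit-check specification, which is not among the documents.

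A PPS effect through EXCL04 or TRT15 is therefore possible but not shown.

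A reader might also take it that the reported counts are bound to be wrong, or read 75% and 25% as misclassification rates. Neither follows. The counts are wrong only if a subject takes one of the nine drugs within the limit, or takes St. John's wort. The percentages describe list entries, not subjects.

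**Conclusion.** The two lists disagree and must be reconciled. As written, the SAP definition can misclassify use in both directions. The fault is established from the text alone and assumes only that SAP Table 2-2 is programmed as it stands.

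The effect on reported counts cannot be sized. It may be zero if nobody used these products.

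The point is minor. It concerns one descriptive summary and leaves the full analysis set, the Week 24 weight endpoint, the dose-response test and its error control untouched.

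**What to change.** Reconcile SAP Table 2-2 with protocol section 5.5.8:

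1. Add St. John's wort, with its coding-dictionary identifier.
2. Move the nine inhibitors out of the prohibited list into a separate block labelled as restricted medication. Report any use there, and flag use beyond the protocol's own 10-day limit.
3. State how days are counted for that flag: whether separate courses are added together, and what happens when a date is partial. One option is to show courses with an incomplete start or end date as duration unknown, so that the section 5.1.3 imputation does not decide the flag.
4. Confirm in the edit-check specification that EXCL04 and TRT15 use the protocol list, and say so in SAP section 5.4.

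If the wider list was deliberate, record it in SAP section 4 and retitle the table accordingly.

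The cost is an edit to one table, a short counting rule, a small programming change and one cross-check. No new data are needed and no clinical rule changes. A separate block is preferable to a bare duration filter because any use remains visible even where its length is uncertain.

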2.5 Analysis of the primary objective

2.5.1 Primary endpoint

The primary analysis variable is the percent change in body weight (kg) from BL at Week 24. BL is defined as the last body weight value measured prior to or at the randomization visit (Visit 201). The analysis will be carried out on the FAS, with missing Week 24 values imputed as described in section 2.5.3.

2.5.2 Statistical hypothesis, model, and method of analysis

The objective of determining a dose response signal and dose-response relationship in either qd or bid dosing regimen compared to placebo will be evaluated using an optimally weighted contrast test following the methodology described in Pinheiro et al. (2006) and Pinheiro et al. (2014). To this end, a candidate model set is defined corresponding to the range of expected mean response in each of the dosing regimen. The candidate model set is used to generate a set of weights for the calculation of optimal contrasts between the responses in the studied dose groups and the placebo group. A statistical test comparing all doses in the different dosing regimens simultaneously to the control group is used, hence a multiplicity adjustment is applied that accounts for the multiple possible dose response behavior considered as well as the common placebo between the dosing regimens. A critical value is derived from a multivariate t-distribution using the correlation matrix induced by the correlations between the weights corresponding to the candidate sets as well as the correlation between the tests of shapes in the dosing regimens to the common placebo group.

Test of the dose response signal

The null hypothesis of a flat dose-response relationship for the percentage reduction in body weight compared to placebo will be tested at a one-sided significance level of 2.5% against the alternative hypothesis of a dose-response relationship leading to a significant decrease in percent body weight.

Hence, the following null and alternative hypotheses will be tested:

- H_01 : there is no dose-response relationship for LIK066 given qd
- H_{11} : there is a dose-response relationship for LIK066 given qd
- H_{02} : there is no dose-response relationship for LIK066 given bid

- H_{12} : there is a dose-response relationship for LIK066 given bid

Given that we suspect the dose-response may behave differently between qd and bid regimens based on the data we have seen from the proof-of-concept study LIK066X2201, we define separate sets for the dose-response candidate models for each dosing regimen. In order to preserve the family-wise error rate at one-sided significance level of 2.5%, the optimal contrasts derived from the model candidate set for each dosing regimen will be individually compared to the critical value derived using a multiplicity adjustment accounts for all tests of comparing LIK066 doses to placebo across regimens simultaneously as described above. The rejection of the null hypothesis for each dosing regimen will be achieved using the maximum test statistic in each dosing regimen from each estimated contrast test in the candidate set.

[figure not shown]
The candidate models generating the contrast weights are described in table 2-3 and depicted in Figure 2-1, with the doses used to define parameters of interest being defined as total daily dose.

The analysis to derive the test statistics is based on an analysis of covariance (ANCOVA) model with the percent change in body weight from BL to Week 24 as a response variable, treatment (placebo and all LIK066 doses from each regimen), stratum indicator (dysglycemic/normoglycemic/T2DM) and region as factors and BL weight as a covariate. Centers will be pooled according to country and region for the purpose of analysis.

Table 2-3 Candidate dose-response models in consideration

#	Candidate models for qd regimen	Candidate models for bid regimen
1	E_{max} model: $ED_{50} = 5$ mg	E_{max} model: $ED_{50} = 5$ mg
2	E_{max} model: $ED_{50} = 50$ mg	E_{max} model: $ED_{50} = 50$ mg
3	Sigmoid E_{max} : $ED_{50} = 75$ mg, $H = 3.5$	Sigmoid E_{max} : $ED_{50} = 75$ mg, $H = 3.2$
4	Sigmoid E_{max} : $ED_{50} = 25$ mg, $H = 0.7$	Linear log-dose: null, $c = 0.8$
5	β -model: $\alpha = 0.8$, $\beta = 0.2$, scale = 180	Linear
6	Exponential: $\lambda = 125$	Quadratic: $\delta = -0.007$

Figure 2-1 Dose-response curve of candidate models (left panel: qd regimen)

The response variable of percent change in body weight from BL to Week 24 used in the above ANCOVA is from an imputed dataset, where the missing Week 24 weight is imputed using the multiple imputation method as described in Section 2.5.3. In order to account for the imputation uncertainty, this ANCOVA model will be repeated for each imputed dataset, which results in a set of least squares (LS) mean estimates for all dose groups for the two regimens and the related covariance matrices. Rubin's rule will be used to combine the multiple sets of LS mean estimates and the related covariance matrices to a single set of LS mean estimates of percent changes of body weight as Week 24 for all dose groups and the related covariance matrix.

The optimal contrasts derived from the candidate model sets will be applied to the combined estimated dose means and covariance matrix to obtain the t statistics for each candidate model in the two regimens and the common critical value $C_{0.025}$. $C_{0.025}$ is the common critical model derived from the reference multivariate t-distribution with the 12×12 correlation matrix induced by testing the candidate dose response models with respect to comparing all candidate models in both dosing regimens to the common placebo group.

The intersection hypotheses H_{01} and H_{02} will be rejected and the statistical significant of dose-response in body weight reduction established if the $\max(t_1, t_2, t_3, \dots, t_{11}, t_{12}) \geq C_{0.025}$. In other words, the intersecting null hypothesis requires the rejection of either H_{01} or H_{02} .

Model averaging to obtain the dose responses for qd and bid dosing regimens

A parametric bootstrap-based model averaging approach will be implemented to obtain the dose response estimates for qd and bid dosing regimens according to the following steps:

1. The parametric bootstrap procedure will draw a sample of mean percent changes in body weight from baseline to Week 24 for all doses (including placebo) from a multivariate normal distribution, with mean and covariance matrix was determined using Rubin's rule, as described earlier. This sample corresponds to the mean response for each dose (including placebo).
2. Model selection will be performed as follows: general dose-response models as specified in Table 2-3 will be fit to this bootstrap sample for qd and bid regimen separately, i.e. Emax, Sigmoid Emax, β -model and Exponential model will be fit to mean response data from placebo and qd doses, and Emax, Sigmoid Emax, Linear log-dose, Linear and Quadratic model will be fit to mean response data from placebo and bid doses. The best model based on the gAIC criterion will be selected for qd and bid regimen separately.
3. After selecting the best models for qd and bid separately, a combined model with parameters corresponding to the individually selected models but with a single parameter for the placebo group will be fitted to the bootstrap sample, i.e. the sampled mean responses for all doses (including placebo).
4. The dose response estimate will be calculated for each dose group, including placebo, using this combined model. The difference in estimated dose response between each dose and placebo will also be calculated. The target doses of interest in each dosing regimen will be calculated based on this common model as well.

5. The above procedure (steps 1-4) will be repeated 5,000 times. The mean dose-response estimates by dose group and mean differences of dose-response estimates between each LIK dose and placebo, the target doses of interest, as well as their 95% confidence intervals will be calculated based on the quantiles (median, 2.5th and 97.5th percentiles) of these multiple sets of dose-response and target dose estimates generated in step 4.

